13.0 Treatment/Follow-up Decision at Evaluation of Patient

NOTE: As of Addendum 4, Event monitoring will no longer be required

- 13.1 After completion of the Day 43 response to vaccine evaluation, patients will discontinue treatment and enter one cycle of OBSERVATION (28 days after end of first cycle +/- 10 days) and then enter EVENT MONITORING.
- 13.2 If Lenalidomide is discontinued due to patient refusal or noncompliance, unacceptable toxicity, or intercurrent illness that makes treatment assessment difficult and the patient received the Prevnar 13 vaccine, they will receive their Day 43 response to vaccine evaluation at which point they will then enter one cycle of OBSERVATION (28 days after end of first cycle +/- 10 days) and then enter EVENT MONITORING.
- 13.3 If a patient on Arm A does not receive the Prevnar 13 vaccine, they will discontinue treatment and go directly to event monitoring per Section 18.0 of the protocol. If a patient on Arm B does not receive the Prevnar 13 vaccine, they will be deemed a cancel and will be removed from the study per Section 13.6 of the protocol.
- 13.4 A patient is deemed *ineligible* if after registration, it is determined that at the time of registration, the patient did not satisfy each and every eligibility criteria for study entry.
 - If the patient received treatment, the patient will go directly to event monitoring. All data up until the point of confirmation of ineligibility must be submitted. Event monitoring will be required per Section 18.0 of the protocol.
 - If the patient never received treatment, on-study material and the End of Active Treatment/Cancel Notification Form must be submitted. No further data submission is necessary.

Note: Due to the nature of the disease, if the patient is diagnosed with DLBCL within the first cycle of treatment, it will be assumed that the DLBCL was present at registration. The patient will be deemed ineligible per Sec 3.29c.
- 13.5 A patient is deemed a *major violation*, if protocol requirements regarding Lenalidomide treatment during Days 1-42 are severely violated such that evaluability for primary end point is questionable. All data up until the point of confirmation of a major violation

must be submitted. The patient will go directly to the event-monitoring phase of the study. Event monitoring will be required per Section 18.0 of the protocol.

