16.321 Disease status by physical exam and complete blood counts will be evaluated in each patient. For CLL, each patient will be classified as CCR, CCRi, PR, SD, or PD per Section 11.2 at the time of the 6 week assessment of immune response. The distribution of disease status will be evaluated in each arm and will be summarized descriptively. Patients will be classified as responders (CCR, CCRi, PR) vs. non-responders (SD, PD). For MBL, patients will be classified as Not PD vs. PD. Differences in disease status response will be compared between the two arms using Fisher's exact test.

16.322 Time to treatment for progressive CLL will be defined as the time from the date of registration to the date of initiation of treatment for progressive CLL. The distribution of time to treatment will be estimated in each arm using the method of Kaplan-Meier. Time to treatment will be compared between the two arms using log-rank statistics.

16.323 Adverse Events: All eligible patients that have initiated treatment will be considered evaluable for assessing adverse event rate(s). Platelets and hemoglobin will be graded according to the Grading Scale for Hematologic Adverse Events in CLL Studies in Appendix IV. The maximum grade for each type of adverse event will be recorded for each patient, and frequency tables will be reviewed for each arm to determine

patterns. Additionally, the relationship of the adverse event(s) to the study treatment will be taken into consideration.

16.33 Correlative Analyses:

16.331 Pre-vaccination (day 15) and day 28 post-vaccination OPA GMTs for each serotype (4, 9V, 23F) will be reported in the vaccine and vaccine + lenalidomide groups. The fold-change in OPA GMT from baseline to 28 days post-vaccination will be evaluated for each serotype, where two-sample t-tests will be used to compare GMTs between the vaccine and vaccine + lenalidomide groups.

16.332 Pre-vaccination (day 15) and day 28 post-vaccination *Streptococcus pneumoniae* serotype specific IgG GMTs for each serotype (1, 3, 4, 5, 6B, 7F, 9V, 14, 18C, 19F, 19A, and 23) will be reported in the vaccine and vaccine + lenalidomide groups. The fold-change in quantitative IgG GMT from pre-vaccine (day 15) to 28 days post-vaccination will be evaluated for each serotype, where two-sample t-tests will be used to compare GMTs between the vaccine and vaccine + lenalidomide groups.

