16.35 Data & Safety Monitoring

16.351 The principal investigator(s) and the study statistician will review the study at least every quarter to identify accrual, adverse event, and any endpoint problems that might be developing. The Mayo Clinic Cancer Center (MCCC) Data Safety Monitoring Board (DSMB) is responsible for reviewing accrual and safety data for this trial at least twice a year, based on reports provided by the MCCC Statistical Office.

16.352 Adverse Event Stopping (applies to each arm independently): The stopping rule specified below is based on the knowledge available at study development. We note that the rule may be adjusted in the event of either (1) the study re-opening to accrual or (2) at any time during the conduct of the trial and in consideration of newly acquired information regarding the adverse event profile of the treatments under investigation.

The study team may choose to suspend accrual because of unexpected adverse event profiles that have not crossed the specified rule below.

Accrual will be temporarily suspended to both arms if at any time we observe events considered at least possibly related to study treatment (i.e. an adverse event with attribute specified as “possible,” “probable,” or “definite”) that satisfy either of the following:

- if 4 or more patients in the first 15 treated patients in either arm experience a grade 4 or higher non-hematologic adverse event at least possibly related to treatment.
- if after the first 15 patients have been treated, 25% of all patients in either arm experience a grade 4 or higher non-hematologic adverse event at least possibly related to treatment.
- Any grade 5 event related to treatment

We note that we will review grade 4 and 5 adverse events deemed “unrelated” or “unlikely to be related”, to verify their attribution and to monitor the emergence of a previously unrecognized treatment-related adverse event.

16.353 Enhanced Safety Monitoring Rule: If at any time after the first 12 patients have been treated on the experimental arm, the rate of grade 3 or 4 non-hematologic adverse events in the experimental arm is \geq 25% higher than the rate in the control arm, the study team will review the adverse events profile in each arm. Accrual may be temporarily suspended to evaluate the types of adverse events and the relation to study treatment.

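### Section 16.323 limits adverse event rates to eligible treated patients, so a patient declared ineligible after exposure drops out of the reported rates but not out of the monitoring rules.

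*Combined protocol and SAP*

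**What the plan says.** Four parts of the protocol bear on who is counted for safety.

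- **Section 16.323 (Adverse Events)** defines the analysis set: "All eligible patients that have initiated treatment will be considered evaluable for assessing adverse event rate(s"). Two conditions apply, eligibility and start of treatment. Maximum grades and frequency tables by arm follow in the same paragraph.
- **Section 13.4** makes eligibility something that can be revised: "A patient is deemed *ineligible* if after registration, it is determined that at the time of registration, the patient did not satisfy each and every" entry criterion. It expects that some of these patients will already have been exposed: "If the patient received treatment, the patient will go directly to event monitoring". On their data it says: "All data up until the point of confirmation of ineligibility must be submitted".
- **The note to Section 13.4** adds a route to ineligibility that starts from an on-treatment diagnosis: "if the patient is diagnosed with DLBCL within the first cycle of treatment, it will be assumed that the DLBCL was present at registration". Such a patient is then ineligible under 3.29c.
- **Sections 16.352 and 16.353** monitor safety on another footing. The first limb of the stopping rule reads: "if 4 or more patients in the first 15 treated patients in either arm experience a grade 4 or higher non-hematologic adverse event". Attribution must be possible or stronger. The second limb takes 25% of all patients in an arm. The enhanced rule in 16.353 starts after 12 patients have been treated on the experimental arm. None of these mentions eligibility.

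A note at the head of Section 13.0 matters for the remedy: "NOTE: As of Addendum 4, Event monitoring will no longer be required".

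**The concern.** A safety set is normally fixed by exposure. Here it also depends on a decision that can be taken after exposure and, in the DLBCL case, one prompted by something diagnosed on treatment. When that happens the patient's whole adverse event record leaves the rates, not only the event that prompted the decision.

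The adverse event profile in each arm is a stated secondary goal (2.23), and Section 16.4 commits to reporting secondary endpoints publicly. The patients are previously untreated, must have none of the listed indications for chemotherapy (3.14), and are not being treated for their underlying disease (11.2). Tolerability will therefore weigh heavily in judging whether the approach deserves further study. Several entry criteria look safety-related (creatinine clearance and platelets in 3.17, cardiac class in 3.23, recent thrombosis in 3.29b), so a patient later found to have failed one may not carry average risk.

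A patient who contributed to a monitoring trigger could also be missing from the final table, leaving the two accounts of the same trial in disagreement.

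**Working it through.** **1. Is there a route back into the rates?** Section 16.323 requires eligibility. Section 13.4 allows eligibility to be withdrawn after treatment and requires data up to that point. No other section returns these patients to the 16.323 rates. The data exist but fall outside the set.

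**2. Who exactly is dropped?** Only patients who are both treated and ineligible. Cancelled patients (13.6) never started treatment. Eligible patients with a major violation, or who took lenalidomide and missed the vaccine, stay in the adverse event set, because 16.323 does not carry the exclusions that 16.311 applies to response.

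**3. Inputs.** Section 16.22 gives 26 evaluable plus 3 extra patients per arm. That reproduces its maximum: 26 + 3 = 29 per arm, and 2 × 29 = 58. The plan states no figure that depends on the adverse event set, so there is none to reproduce. The number of treated-but-ineligible patients is not given; I assume one per arm and show up to three. Three is a ceiling (3/29 = 10.3% of an arm), since the allowance also covers cancellation, major violation and missed vaccine.

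**4. One grade 4 event, in the one ineligible patient of an arm of 29.**

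- Kept: 1/29 = 3.4%. The exact (Clopper-Pearson) lower limit is 1 − 0.975^(1/29) = 0.1%. The upper limit solves (1 − p)^29 + 29p(1 − p)^28 = 0.025, giving 17.8%.
- Dropped: 0/28. The upper limit is 1 − 0.025^(1/28) = 12.3%.

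**5. Direction.** With *e* events among *n* treated patients and *d* dropped, the eligible-only rate is (*e* − *d*)/(*n* − *d*) if every dropped patient had an event and *e*/(*n* − *d*) if none did. For *e* = 8 and *n* = 29, all treated patients give 8/29 = 27.6%.

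| Dropped | All had an event | None had an event |
|---|---|---|
| 1 | 7/28 = 25.0% | 8/28 = 28.6% |
| 2 | 6/27 = 22.2% | 8/27 = 29.6% |
| 3 | 5/26 = 19.2% | 8/26 = 30.8% |

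**6. Against the stopping boundary.** Four events in 15 treated patients is 26.7% and triggers 16.352. If one of the four is later found ineligible, 16.323 would show 3/14 = 21.4% for the same patients. The trigger itself is unaffected, because 16.352 counts treated patients.

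**The case against.** The best case on the other side is that this is a wording point with little practical reach, and much of that stands.

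- Eligibility is checked before a registration is accepted (6.14), so treated-but-ineligible patients should be uncommon. The documents give no expected number.
- The events are not lost to oversight. Expedited reporting (10.4), death reporting (10.52), routine reporting (10.6), the quarterly team review and the twice-yearly DSMB review (16.351) carry no eligibility condition. A reader might infer that safety monitoring is weakened or that a stopping decision could be missed; the text does not support that.
- A reader might infer that toxicity will be understated. Step 5 shows that the rate rises when the dropped patients had no event, so the direction cannot be known in advance.
- A reader might compare 1/29 with 0/26 (upper limit 13.2%). That would need all three extra patients in an arm to be both treated and ineligible; 26 is the target for the response endpoint, not the adverse event set.
- The DLBCL provision is weak evidence of a hidden drug effect, because the protocol presumes the lymphoma predated registration. What remains is that the patient's other adverse events leave the rates as well.
- Adding these patients to the denominator has its own cost. Their data are required only up to confirmation of ineligibility, so later adverse event assessments may be missing, and incomplete observation can dilute a rate.

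None of this gives a reason for the eligibility condition itself. Restricting the response analysis to eligible patients is a separate efficacy choice and does not carry over to safety.

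**Conclusion.** The point holds in a limited form. Section 16.323 makes the reported adverse event rates depend on eligibility findings that can follow exposure, while 16.352 and 16.353 do not. With one such patient in an arm of 29, a single grade 4 event moves from 3.4% to zero observed in 28; the bias can go either way. The size rests on an assumed number of treated-but-ineligible patients, and the effect is nil if there are none.

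Section 16.352 does not define a treated patient. Reading it as restricted to eligible patients would remove the mismatch, but only by adding a condition that is not in the text.

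The consequence is confined to the 16.323 rates and tables. No sample size, hypothesis test or stopping decision changes. It merits correction because the better definition costs very little.

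**What to change.** In 16.323, define the adverse event set as all patients who received any dose of lenalidomide or the vaccine, whatever their later eligibility status, reported by arm. State in 16.352 and 16.353 that they use the same set. An eligible-only table may be added as a supplement. There is no need to regroup patients by treatment received: the documents show no crossover problem, and doing so could move an Arm A patient who received only the vaccine into the control arm's safety table.

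The cost is one changed sentence and one cross-reference. Sample size, treatment and visits stay as they are, and 13.4 already requires data up to confirmation of ineligibility. The downside is incomplete follow-up: nothing beyond that point is required, and event monitoring ended with Addendum 4. The tables should mark the patients whose observation was cut short and give the last adverse event assessment available for each, so that a missing later assessment is not read as the absence of an event.

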10.41 Special Situations for Expedited Reporting

Exceptions to Expedited Reporting: EXPECTED Serious Adverse Events

An expedited report may not be required for specific Grade 1, 2, 3 and 4 Serious Adverse Events where the AE is **EXPECTED**. Any protocol specific reporting procedures **MUST BE SPECIFIED BELOW** and will supercede the standard Expedited Adverse Event Reporting Requirements. Note: These adverse events must still be reported through the routine reporting mechanism [i.e. Nadir/Adverse Events Form]; see footnote 1.

CTCAE Category	Adverse Event	Grade	Attribution	Comments
Blood and lymphatic system disorders	Anemia	3 or 4	All	This frequent event in patients with CLL will be reported through the routine reporting mechanism
Investigations	Platelet count decreased	3 or 4	All	This frequent event in patients with CLL will be reported through the routine reporting mechanism
	Neutrophil count decreased	3 or 4	All	This frequent event in patients with CLL will be reported through the routine reporting mechanism
	Lymphocyte count decreased	3 or 4	All	This frequent event in patients with CLL will be reported through the routine reporting mechanism
	White blood cell decreased	3 or 4	All	This frequent event in patients with CLL will be reported through the routine reporting mechanism

¹ These exceptions only apply if the adverse event does not result in hospitalization. If the adverse event results in hospitalization, then the standard expedited adverse events reporting requirements must be followed.

Specific protocol exceptions to expedited reporting should be reported expeditiously by investigators **ONLY** if they exceed the expected grade of the event.

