10.6 Required Routine Reporting

Adverse events to be graded at each evaluation (e.g. day 15, day 43, and observation) and pretreatment symptoms/conditions to be evaluated at baseline per Common Terminology Criteria for Adverse Events (CTCAE) v4.0 grading unless otherwise stated:

System Organ Class (SOC)	Adverse Event/Symptoms	Baseline	Day 15, Day 43, and Observation
Investigations	Platelet count decreased**	X	X
General disorders and administration site conditions	Fever	X	X
	Fatigue	X	X
Blood and lymphatic system disorders	Febrile neutropenia	X	X
	Anemia**	X	X
Skin and subcutaneous tissue disorders	Rash maculo-papular	X	X
Neoplasms benign, malignant and unspecified (incl cysts and polyps)	Tumor pain*		X

* Tumor flare reactions will be classified under tumor pain and graded based on CTCAE v4.0.

** Grading will be performed by the study statisticians at the time of analysis based on the CLL toxicity grading scale for blood counts in Appendix IV. CTCAE grades for platelet count decreased and anemia will also be recorded for reporting purposes.

10.61 Submit via appropriate MCCC Case Report Forms (i.e., paper or electronic, as applicable) the following AEs experienced by a patient and not specified in Section 10.6:

10.611 Grade 2 AEs deemed *possibly, probably, or definitely* related to the study treatment or procedure.

10.612 Grade 3 and 4 AEs regardless of attribution to the study treatment or procedure.

10.613 Grade 5 AEs (Deaths)

10.6131 Any death within 30 days of the patient's last study treatment or procedure regardless of attribution to the study treatment or procedure.

10.6132 Any death more than 30 days after the patient's last study treatment or procedure that is felt to be at least possibly treatment related must also be submitted as a Grade 5 AE, with a CTCAE type and attribution assigned.

10.62 Refer to the instructions in the Forms Packet (or electronic data entry screens, as applicable) regarding the submission of late occurring AEs following completion of the Active Monitoring Phase (i.e., compliance with Test Schedule in Section 4.0).

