11.4 Definitions

The NCI Working Group criteria (Hallek, 2008) will be used to assess response to therapy.

11.41 COMPLETE CLINICAL RESPONSE (CCR) requires all of the following at the Day 43 evaluation:

11.411 Absence of lymphadenopathy (e.g. lymph nodes >1.5 cm) by physical examination.

11.412 No hepatomegaly or splenomegaly by physical examination.

11.413 Absence of constitutional symptoms.

11.414 CBC demonstrating:

- Peripheral blood lymphocytes <4000/ μ L.
- Neutrophils >1500/ μ L
- Platelets >100,000/ μ L (untransfused).
- Hemoglobin >11.0 g/dL (untransfused).

Note: Patients who fulfill all criteria for a CCR but who have a persistent anemia, thrombocytopenia, or neutropenia related to drug toxicity rather than residual CLL will be classified as **CCR with incomplete marrow recovery (CCRi)** according to the international criteria (Hallek, 2008).

- 11.42 **PARTIAL RESPONSE (PR)**: PR requires the patient exhibits at least two of the features in Sections 11.421, 11.422, and 11.423 below (**if** abnormal prior to therapy) as well as **one or more** of the remaining features (Sections 11.424, 11.425, 11.426) at the day 43 evaluation. For patients with Rai stage 0 disease (e.g. no palpable nodes or organomegaly) and those with MBL a 50% reduction in lymphocytosis will be considered to represent a PR. In addition to the parameters listed below, the presence or absence of constitutional symptoms will be recorded.
- 11.421 $\geq 50\%$ decrease in peripheral blood lymphocyte count from the pretreatment baseline value.
- 11.422 $\geq 50\%$ reduction in the sum of the products of the maximal perpendicular diameters of the largest measured node or nodal masses in the right and left cervical, axillary, and inguinal lymph node regions on physical examination.
- 11.423 $\geq 50\%$ reduction in size of liver and/or spleen as measured by physical exam noting the maximal distance below the respective costal margins of palpable hepatosplenomegaly during rest.
- 11.424 Neutrophils $>1500/\text{ul}$ or 50% improvement over baseline.
- 11.425 Platelets $>100,000/\text{ul}$ or 50% increase over baseline.
- 11.426 Hemoglobin $>11.0 \text{ gm/dl}$ or 50% increase over baseline without transfusions.
- 11.43 **PROGRESSION (PD)**: Patients will be considered to have PD according to the NCI criteria²⁴ if they experience any of the following:

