Appendix IV
Grading Scale for Hematologic Toxicity in CLL Studies¹

Decrease from Pretreatment value (%)	Grade ²	
	Platelets ^{3, 5}	Hemoglobin ^{4, 5}
No change - 10%	0	0
11-24%	1	1
25-49%	2	2
50-74%	3	3
≥ 75%	4	4

1. A decrease in circulating granulocytes is not being considered since it is not a reliable index in CLL.
2. Grades: 1–mild; 2–moderate; 3–severe; 4–life–threatening. Grade 5 (fatal) toxicity can potentially occur at any level of decrease from pretreatment values and will be recorded as such.
3. If, at any level of decrease the platelet count is $<20,000/\mu\text{L}$, this will be considered grade 4, unless the initial platelet count was $\leq 20,000 \mu\text{L}$ in which case the patient is inevaluable for toxicity referable to platelet counts.
4. Baseline and subsequent hemoglobin determinations must be immediately prior to any given transfusions.
5. If, at any level of decrease from the baseline value the platelet and/or hemoglobin counts are within normal limits, this will be considered a grade 0.

* Hallek BD, et al.: Guidelines for the diagnosis and treatment of chronic lymphocytic leukemia: a report from the International Workshop on Chronic Lymphocytic Leukemia updating the National Cancer-Institute- Working Group 1996 guidelines: Blood 111:54465456, 2008.

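### Cheap improvement: required reporting of grade 2 neutropenia depends on investigator attribution in a trial without placebo, although scheduled blood counts in both arms could be graded directly

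*Combined protocol and SAP*

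**What the plan says.** Three parts of the plan govern neutrophil events.

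- **Solicited terms (10.6).** Platelet count decreased, anemia and febrile neutropenia are graded at every evaluation. Neutrophil count decreased is not listed. For platelets and anemia the footnote adds that "Grading will be performed by the study statisticians at the time of analysis", and CTCAE grades are recorded for those two as well.
- **Unlisted terms (10.61).** Sites must submit "Grade 2 AEs deemed *possibly, probably, or definitely* related to the study treatment or procedure" and "Grade 3 and 4 AEs regardless of attribution to the study treatment or procedure". Grade 1 is not mentioned.
- **Analysis (16.323).** "Platelets and hemoglobin will be graded according to the Grading Scale for Hematologic Adverse Events in CLL Studies in Appendix IV". The maximum grade of each event type is tabulated by arm. No neutrophil grade is derived from counts, and no shift from baseline is planned.

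The plan gives a reason for leaving neutrophils off the percent-decrease scale. Appendix IV, footnote 1, states: "A decrease in circulating granulocytes is not being considered since it is not a reliable index in CLL".

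Elsewhere the absolute neutrophil count and its CTCAE grade are used. Section 10.1 adopts CTCAE v4.0 for all adverse event reporting. Section 8.2 interrupts lenalidomide at grade 3 or higher. Section 10.41 waives only the expedited report for grade 3-4 decreases without hospitalization, noting that "These adverse events must still be reported through the routine reporting mechanism". Disease status uses neutrophils too: the partial response criterion in 11.424 allows "or 50% improvement over baseline", and the note on incomplete marrow recovery in 11.41 refers to "neutropenia related to drug toxicity rather than residual CLL".

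**The concern.** Goal 2.23 is to describe the adverse event profile in each arm, and 15.17 lists neutropenia as very common (at least 10%) with lenalidomide. Arm A takes lenalidomide. Arm B receives the vaccine alone, with no placebo (7.1), so the person judging relatedness knows whether the patient is taking a drug that lowers neutrophil counts. The same grade 2 count may then be called possibly related in Arm A and unrelated in Arm B, and only the first must be submitted.

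Baseline adds a second difficulty. Section 3.17 admits patients with an ANC as low as 1000/mm³, below the 1500/µL that 11.414 and 11.424 use as a response cut-off. Some low counts may therefore predate treatment. Without a baseline neutrophil grade, the planned table cannot separate these from new falls.

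At stake is how far readers can rely on the grade 2 neutropenia line in a descriptive secondary safety table.

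**Working it through.** The plan states no figure on this point, so there is none to reproduce. The check traces the rules and then sizes the available data.

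**1. Which neutrophil events must be submitted**

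| Event | Rule | Depends on attribution? |
|---|---|---|
| Grade 1 | Not required (10.61) | No |
| Grade 2 | Required if at least possibly related (10.611) | Yes |
| Grade 1-2 with hospitalization of 24 h or more, within 30 days of last administration | Reported through 10.4, then routinely (10.11) | No |
| Grade 3-4 | Required (10.612; 10.41 waives only the expedited report) | No |
| Febrile neutropenia | Solicited at each evaluation (10.6) | No |

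The attribution filter therefore acts on grade 2 events without hospitalization. These rules are a minimum; sites may submit more.

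**2. Whether grades could be derived without attribution**

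The test schedule (4.0) has a CBC with differential at baseline, Day 15, Day 43 and Observation, not restricted to Arm A. The counts are thus scheduled alike in both arms. Section 8.2 adds weekly neutrophil rechecks, but only for lenalidomide patients whose drug is interrupted, so including those would create a new imbalance.

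**3. How a difference could arise**

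Suppose both arms have the same true grade 2 rate g, and a case is attributed with probability a_A in Arm A and a_B in Arm B. The expected difference in submitted rates is g × (a_A − a_B), although the true difference is 0. With assumed values:

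- g = 10%, a_A = 0.5, a_B = 0.1: 0.10 × 0.4 = 4 percentage points.
- g = 30%, a_A = 0.9, a_B = 0: 0.30 × 0.9 = 27 percentage points.

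None of g, a_A or a_B is in the documents. The range shows the mechanism only and does not estimate the bias in this trial.

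**4. Data already scheduled**

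Section 16.22 plans 52 evaluable patients and a maximum accrual of 58.

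- Post-baseline counts for 52 patients: 52 × 3 = 156; without Observation, 52 × 2 = 104.
- For 58 patients: 58 × 3 = 174; without Observation, 58 × 2 = 116. These are ceilings, because the extra six allow for ineligibility, cancellation, violation or no vaccine.

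**5. Precision of the proposed table**

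With equal true rate p and n per arm, the 95% half-width for an arm difference is 1.96 × √(2p(1−p)/n). The rates are assumed; n = 26 is the plan's target and n = 29 its ceiling.

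| p | n = 26 | n = 29 |
|---|---|---|
| 5% | 11.8 points | 11.2 points |
| 10% | 16.3 points | 15.4 points |
| 15% | 19.4 points | 18.4 points |

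At p = 5% and n = 26 only 26 × 0.05 = 1.3 events are expected per arm, so the normal approximation is rough there. The table would describe the arms but could not settle a comparison.

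**The case against.** The strongest reply is that the omission is deliberate. Appendix IV calls a granulocyte decrease unreliable in CLL, and that reason could extend to low-grade CTCAE shifts. Section 8.2 uses the neutrophil grade only from grade 3 upward, and 10.41 lists only grades 3-4, so neither shows that the sponsor wanted grades 1-2. Much of this stands: the footnote is a stated reason, the percent-decrease scale should be left alone, and any new table needs a caveat. The footnote does not settle the matter, however. Under 10.1 and 10.611 related grade 2 neutropenia already enters the 16.323 tables on the CTCAE scale. The choice is between tabulating grade 2 by attribution and tabulating it by count.

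Second, the clinically important events are captured already. That is correct, and it is why the point is minor.

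Third, the grade 2 filter covers every unlisted term, and liver enzymes, creatinine and potassium are scheduled as well. Also true. Neutrophils come first because 8.2 names them as a dosing trigger and neutropenia is a listed very common effect; that is a judgment of priority.

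Fourth, Arm B's first study treatment is the Day 15 vaccine, so its Day 15 count may precede any treatment. This stands, and the table has to show it.

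A reader might infer that all reporting below grade 3 turns on attribution, that the plan overlooked neutropenia, or that the safety comparison is known to be distorted. The documents support none of these. Grade 1 is simply not required, hospitalized cases are reported regardless, the exclusion from Appendix IV is explained, and no attribution rates are given from which a distortion could be calculated.

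**Conclusion.** The point holds as an optional, low-cost improvement. Followed as written, the plan can give a grade 2 neutropenia frequency that is ascertained differently by arm, because submission is required only after a relatedness judgment made without a placebo control. The size of any bias cannot be estimated: the documents give no neutropenia rate for 2.5-5 mg over six weeks, no split by grade and no attribution share.

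The consequence is confined to a descriptive secondary table. Section 16.323 plans no test of adverse events, the rate-based rules in 16.352 and 16.353 count non-hematologic events only, and the primary analysis does not use neutrophils. It would go too far to say that serious neutropenia could be missed through the attribution filter, since 10.612 and the solicited febrile neutropenia item prevent that.

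The conclusion assumes that sites submit roughly what 10.61 requires and that attribution of a low count may differ by arm. The low cost assumes that ANC values are in the database.

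**What to change.** Add to 16.323 that, for eligible treated patients in both arms, CTCAE v4.0 neutrophil grades will be derived from the scheduled baseline, Day 15 and Day 43 counts, and from Observation if that differential is entered. Then:

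- Report by arm, descriptively, the worst post-baseline grade and the shift from baseline.
- Show Day 15 and Day 43 separately as well, because the Arm B Day 15 count may precede the vaccine.
- Put investigator-submitted neutropenia on its own line.
- Exclude the unscheduled weekly rechecks under 8.2.
- Leave Appendix IV unchanged, and footnote the table to say that ANC is a less specific marker of toxicity in CLL.

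The cost is a short SAP addition and one table, with no new visits or tests. Confirm first that ANC is entered on the laboratory forms. Baseline and Day 43 neutrophils are already needed for CLL/SLL disease status (11.414, 11.424), but the fields of the Interval Laboratory form are not shown, so entry of Day 15, Observation and MBL values is unconfirmed. If Observation is not entered, omit it rather than change a form.

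The downsides are one more imprecise table, low points missed between visits, and low-grade rates that may look less favorable than submitted events alone.
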